## 9.5 Randomization and Blinding

Enrolled participants will not be randomized, as this is by necessity an open-label study. This will be an unblinded study.

#### 9.6 Data Analysis

For primary endpoints, sensitivity analyses will be performed by age group (15 to 19-year-old YMSM; 20 to 24-year-old YMSM). PK estimates will be reported overall and per group, given need to examine whether there are significantly different TFV-DP rectal tissue levels across these two age groups. Safety data will be reported in the aggregate for the overall population, as safety is not expected to differ significantly by age group. As noted above, sample size is conditioned to a great degree on having a comparable, complete, and relevant cohort for comparison to DREAM-01. Descriptive statistics and graphics will be used to summarize the characteristics of endpoints across each step of the study. Continuous measures will be summarized by

means and standard deviations or median and interquartile range depending on data distribution. For binomial endpoints, 95% exact confidence intervals will be calculated. Given the small sample size and possible non-normality of the data, non-parametric tests will be used to test for differences among (Kruskal-Wallis) and between (Wilcoxon rank sum test) test formulations.

Willingness to engage in biomedical clinical trials: We will examine YMSM's willingness to engage in biomedical clinical trials through several data sources, including: IDIs from YMSM who screen in-person yet refuse to enroll in the Phase I Trial (n=32), as well as trial participants' experiences in the trial and future willingness to participate in future biomedical trials (n=16). We will use semi-structured guides in the videoconferencing interviews to examine YMSM's perceived benefits and barriers to participating in a clinical trial, identify challenges and opportunities to ensure inclusion of YMSM in biomedical trials, and explore youth-driven perspectives on what strategies could optimize participation in future biomedical trials. Research assistants at the University of Pennsylvania will format all transcripts and import them into Dedoose, a platform commonly used to organize and manage qualitative data. We will approach the data from a phenomenological framework given our interest in understanding the lived experiences of YMSM in their communities. Initial reading and open coding of the transcripts will be done by the primary analysis team at the University of Pennsylvania, and brought to meetings for review, comparison, and refinement. As thematic codes are identified in the data, they will be included in the codebook. This systematic process will lead to the creation of a coding structure that will involve a hierarchical set of constructs that account for the patterns seen in the data. After creating a codebook, we will code several transcripts jointly as a team to ensure that the meaning, interpretation, and analytic approach are uniform across coders. We will discuss themes, resolve difficulties or concerns that may arise while coding, and make changes accordingly. Comparative analyses will be conducted to clarify differences among subgroups of YMSM (e.g., YMSM under age 20 vs those who are 20 or over). The use of negative case analysis and testing of rival hypotheses are methodological strengths that ensure the credibility and trustworthiness of the data.

Acceptability: To examine the YMSM's overall product acceptability of the TFV douche formulation after rectal administration, as determined by participants' self-report of likelihood of product use if shown to be effective, we will examine the outcome in both continuous and dichotomous forms. We define the acceptability as a mean score of 3 or higher on 4-point continuous acceptability measures (1= completely unacceptable; 2= somewhat unacceptable; 3= somewhat acceptable; 4= highly acceptable) that we argue is the minimal clinically meaningful threshold for acceptability. Under such design, we will test the null hypothesis that the testing product has a true mean acceptability score greater than or equal to 3. If the null hypothesis is rejected, we will conclude that the product under consideration does not have good acceptability in the current format among YMSM. Conversely, if the null hypothesis is not rejected, we cannot rule out the possibility of a truly acceptable product and further confirmatory testing would be of interest. In such case, the Type I error is the probability that we mistakenly declare the testing product is not acceptable when in reality it is acceptable. We will conduct a one-sample, one-sided t-test to test above null hypothesis. We will also conduct a paired-sample t-test to determine whether YMSM's acceptability of a TFV douche changed between before and after using it. As is conventional in early phase trials, we set the type I error at 0.10 and will not adjust for multiple comparisons. Trial participants will complete an IDI (~45 minutes) at the Termination Visit. This IDI will include questions exploring user-centered suggestions for product design and delivery, acceptability and influence to use the study product in the future, douching history and education, and experiences participating in the study, among other topics. Suggestions for product improvement will also be collected. Major components of both survey and IDI assessments have been used successfully and validated in prior ATN and rectal microbicide trials (e.g., MTN-006, MTN-007, MTN-017, MTN-026, MTN-033) by [name], and are currently being used in MTN-035.

Safety: To evaluate the safety of a single dose of a TFV douche when applied rectally, as measured by the number of  $\geq$ Grade 2 adverse events (AEs) as defined by the Division of AIDS Table for Grading the Severity of Adult and Pediatric Adverse Events. For the safety analysis, the number and the frequency of all adverse events (AEs) will be tabulated. A single summary outcome of this type (yes/no) can be reasonably assumed to follow a Bernoulli distribution. Assuming a true underlying rate of one or more participants experiencing AEs is between 0.01 and 0.20 in a sample of 16 YMSM, there would be a 81% chance that one or more participants might experience an AE when the true rate is at least 10% and a probability less than 15% when the true rate is no more than 1%. Unless the true rate is at least 3%, the probability of two or more subjects experiencing AEs will be quite small – less than 5%. Additional safety analyses will also tabulate the number and type of AEs observed overall, and by severity, site, and study product. AEs that lead to discontinuation of study participation will be tabulated separately.

Pharmacokinetics: To characterize the systemic and compartmental pharmacokinetics of a TFV douche following rectal application, as measured by TFV concentrations in plasma, rectal fluid and rectal mucosal tissue homogenates and cells. Pharmacokinetic parameters will be compared to data from studies using rectal dosing of TFV in DREAM-01 and other oral TFV dosing studies in adults, which also included colorectal biopsies. Pharmacokinetics in blood plasma and PBMCs, colon tissue homogenate and cells, and rectal fluid for the TFV-based douche will be evaluated after rectal administration. The primary analysis will use noncompartmental methods to estimate pharmacokinetic parameters, including peak concentration (Cmax, time to peak concentration ( $T_{max}$ ), area under the matrix concentration-time curve from 0 to infinity ( $0 \rightarrow \infty$ ), and terminal elimination half-life. For sparsely sampled matrices (colon tissue homogenate, colon tissue cells, and rectal fluid), we will use population PK methods to build PK models describing individual PK parameter estimates and typical values for the population along with significant covariates (possibly weight, age, pharmacogenetics, creatinine clearance). Tenfovir and TFV-DP assays will be performed by the Clinical Pharmacology Analytical Laboratory (CPAL) at Hopkins and are validated following FDA bioanalytical guidance and approved by an NIH-cross network Clinical Pharmacology Quality Assurance (CPQA) program before used in clinical studies. Primary PK analyses will be testing for (1) differences in PK measures between the two age groups (Kruskal-Wallis) and (2) comparison with DREAM-01 PK results.

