#### 2.2 Primary Endpoints

#### Acceptability

Participant self-report of product acceptability, liking the product, and likelihood of use in the context of receptive anal intercourse

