### 9.3 Study Hypotheses

This protocol and derived data will provide information that will address, even if not completely answer, the following study hypotheses:

- YMSM will find the product to be acceptable and behaviorally congruent with their rectal hygiene practices
- The TFV douche will be safe and acceptable when applied rectally
- The TFV douche will exceed target colon MMC concentrations for a period of 1 hour to 72 hours postdose
- Concentrations in various compartments after enema will provide an important parallel to concentrations seen after TFV gel (historic control from previous study) and will provide correlating data to a prior study carried out in adult MSM.

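### The primary acceptability test can screen the douche out but can never support the hypothesis that it is acceptable, and its chance of missing a product below the threshold is not stated

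*Combined protocol and SAP*

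**What the plan says.** The first study hypothesis in section 9.3 is that "YMSM will find the product to be acceptable and behaviorally congruent with their rectal hygiene practices". Section 9.6, under Acceptability, fixes the threshold: "We define the acceptability as a mean score of 3 or higher on 4-point continuous acceptability measures". The anchors run from completely unacceptable (1) to highly acceptable (4), and the plan calls 3 the smallest clinically meaningful level.

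The same paragraph makes that level the null: "we will test the null hypothesis that the testing product has a true mean acceptability score greater than or equal to 3". It continues: "We will conduct a one-sample, one-sided t-test to test above null hypothesis", and "we set the type I error at 0.10 and will not adjust for multiple comparisons". On rejection, "we will conclude that the product under consideration does not have good acceptability in the current format among YMSM". On non-rejection the plan claims only that an acceptable product remains possible and that confirmatory testing would be worthwhile. It defines its type I error as wrongly discarding an acceptable product.

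On what is measured, section 9.6 says acceptability is determined by "self-report of likelihood of product use if shown to be effective", yet the four anchors are acceptability anchors. Section 2.2 lists "Participant self-report of product acceptability, liking the product, and likelihood of use" as the endpoint, and section 6.12.2 gives product acceptability and likelihood of future use as separate questionnaire domains.

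**The concern.** Acceptability is the first-listed primary objective, and the protocol attaches a formal test to it. The hypothesis in section 9.3 sits inside the null of that test. A null can fail to be rejected but cannot be supported that way, so a sample mean of 3.8 and a sample mean of 2.9 could receive the same formal statement.

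The alpha of 0.10 limits one error, discarding an acceptable product. The opposite error, carrying forward a product whose true mean is below 3, has no stated limit, no assumed SD and no alternative mean. It grows as the sample shrinks or the scores become more variable. The only power statement in the plan (section 9.4) concerns a two-group comparison with DREAM-01 and does not apply here.

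The paragraph also leaves open which questionnaire item is compared with 3, so the primary result could be computed in more than one way.

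**Working it through.** **Inputs.** Threshold 3, one-sided lower-tail t-test and alpha 0.10 (section 9.6); n = 16 (section 9.4). The SD is not in the documents, so 0.6, 0.8 and 1.0 are assumed. The plan gives no operating characteristic for this test, so there is no figure of its own to reproduce.

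**Rule as written.** With 15 degrees of freedom the critical value is 1.341. The null is rejected when (mean − 3)/(s/√16) < −1.341, that is, when the observed mean falls below 3 − 1.341·s/4. For s = 0.6, 0.8, 1.0 that cut-off is 2.80, 2.73, 2.66.

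**Chance of not being screened out.** For true mean μ and SD σ, the statistic follows a noncentral t with 15 df and noncentrality δ = (μ − 3)/(σ/4). The probability of not rejecting is 1 − F(−1.341; 15, δ). At μ = 3 it is 0.90, which agrees with the stated alpha. Example: μ = 2.8, σ = 0.8 gives δ = −0.2/0.2 = −1.0 and a probability of 0.621.

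| True mean | SD 0.6 | SD 0.8 | SD 1.0 |
|---|---|---|---|
| 2.8 | 49.4% | 62.1% | 69.3% |
| 2.7 | 25.4% | 43.0% | 54.6% |
| 2.6 | 9.5% | 25.4% | 39.2% |
| 2.5 | 2.5% | 12.5% | 25.4% |

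Non-rejection is more likely than not only when the true mean lies within about one third of an SD of 3 (above 2.80, 2.74, 2.67 for the three SDs). Rejection reaches 80% at about 0.55 SD below 3 (2.67, 2.56, 2.45).

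**Smaller samples.** With 14 evaluable (section 4.4 targets 90% retention; 0.9 × 16 = 14.4), a true 2.8 is not screened out 53%, 65%, 71% of the time. Section 9.6 also plans age-group sensitivity analyses of the primary endpoints. With 8 per group, a true 2.5 is not screened out 18%, 35%, 48% of the time.

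**Adding a lower-bound criterion.** *Acceptable* is declared when the lower one-sided 90% bound, mean − 1.341·s/4, exceeds 3. The observed mean must then exceed 3.20, 3.27, 3.34. The probability is 1 − F(1.341; 15, δ). Under the resulting three-way rule (SD 0.6 / 0.8 / 1.0):

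| True mean | Not acceptable | Inconclusive | Acceptable |
|---|---|---|---|
| 2.8 | 50.6 / 37.9 / 30.7% | 48.9 / 60.9 / 67.3% | 0.5 / 1.2 / 2.0% |
| 3.2 | 0.5 / 1.2 / 2.0% | 48.9 / 60.9 / 67.3% | 50.6 / 37.9 / 30.7% |
| 3.5 | below 0.1% | 2.5 / 12.5 / 25.4% | 97.5 / 87.5 / 74.6% |

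**Check on normality.** Simulation with discrete 1-4 scores at n = 16 gives a similar picture. A distribution with mean 2.75 and SD 0.89 is not screened out 60% of the time, and one with mean 2.5 and SD 0.92 is not screened out 21%. At a true mean of 3 the lower-bound criterion declares *acceptable* about 11% of the time, close to the nominal 10%.

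**The case against.** The strongest defence is that the plan does what it says. It describes a screening rule, states which error it controls, and does not call non-rejection proof of acceptability. Section 2.1 words the objective as descriptive, section 9.1 calls the study exploratory, and section 9.3 admits that the hypotheses may not be fully answered. In a 16-person Phase I study, choosing to guard against discarding a good product is a legitimate preference. All of this stands, and it means that the plan contains no concealed false claim.

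A reader might infer that a product below the threshold usually passes. The figures do not support that as a general statement: it holds only for shortfalls under about one third of an SD, and a true 2.5 is screened out 75% to 97.5% of the time over the assumed SDs. A reader might also infer that the rule favours the product. The plan draws no positive conclusion from non-rejection, and under the proposed rule a true 2.8 would still be *inconclusive* 49% to 67% of the time. The amendment adds a positive category; it does not make the screen stricter.

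The plan also promises other output: continuous and dichotomous summaries, exact intervals for binomial endpoints, a before-after paired test and interviews. A high mean would therefore be visible in the report. It would still have no pre-specified criterion for support, and the cut-point of the dichotomy is not given.

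Finally, a reader might infer that the threshold sits on a scale that does not measure the outcome. The questionnaire items are not in the documents and section 9.6 refers to measures in the plural, so only ambiguity about the tested item is established.

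**Conclusion.** The point holds as a mismatch between hypothesis and test. The test in section 9.6 cannot support the first hypothesis in section 9.3, whatever the data, and the error of failing to screen out a product below 3 is unstated. Over the assumed SDs of 0.6 to 1.0 that error is 49% to 69% at a true mean of 2.8 and 2.5% to 25.4% at 2.5, with n = 16 and approximate normality. The structural conclusion does not depend on the SD; every percentage does.

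This should be corrected, but it does not threaten the trial: no data are lost, and the plan's wording on non-rejection is already cautious. The question of which item is tested needs clarification and is not shown to be an error.

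**What to change.** In section 9.6, replace the two-outcome rule with three outcomes, using the same threshold, alpha and sample:

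- *Not acceptable* if the upper one-sided 90% confidence bound for the mean is below 3. This is the existing test.
- *Acceptable* if the lower one-sided 90% confidence bound exceeds 3.
- *Inconclusive* otherwise.

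Report the mean with both bounds (together a two-sided 80% interval), and state the assumed SD range and the resulting probabilities, for example the tables above. Name the single post-dose item that is compared with 3 and give its anchors. If that item is acceptability, report likelihood of use separately on its own response scale. Do not present a post-dose likelihood proportion as matching the 15 of 17 quoted for DREAM-01 in section 1.6, because that figure is anticipated use at baseline.

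The cost is wording only, with no new data and no change in sample size. The drawback is that a product truly at 3.2 earns a positive statement only 51%, 38% or 31% of the time (SD 0.6, 0.8, 1.0). That is a fair reflection of what 16 participants can show.

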#### 2.1 Primary Objectives

#### Acceptability

To describe YMSM's acceptability of a novel HIV prevention douche, prior to and after using a one-time dose of the Product C douche.

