## 6.3 Visit 1: Screening Visit

A Screening Visit will take place up to 45 days prior to the Enrollment Visit. The study team will explain the procedures for the Phase I Safety and Acceptability Trial, and answer questions from prospective participants.

At this visit, YMSM ( $n\approx48$ ) will be consented to participate in Screening Procedures, which includes HIV/STI testing, and a brief, online survey regarding their sexual behaviors, prior experiences and comfort using rectal products, and douching or other rectal hygiene practices. Only participants who consent to participating in the Phase I trial will then undergo a medical exam. It is important to underscore that participants receive risk reduction counseling as part of both screening and enrollment procedures, including condoms and lube and discussion with site staff about daily oral PrEP.

YMSM who are <18 years old must be accompanied by a parent/guardian at this visit. Written informed consent will be obtained at the screening before any procedures are initiated. For participants who do not meet the eligibility criteria, screening will be discontinued once ineligibility is determined. Participants not meeting the eligibility criteria may be rescreened later, if appropriate, as in the case of a concomitant medication washout period. In such cases, the length of the washout period will be determined by the PI based on safety considerations and the elimination half-life of the concomitant medication. Screening labs may be repeated to determine eligibility.

- YMSM consenting and found to be evaluable for participation in the Phase I Trial (n≈16) will be scheduled for their Dosing visit once all HIV/STI labs have been confirmed, leaving no more than 45 days between the Screening and Baseline visits.
- YMSM not interested in enrolling or not eligible for enrollment in the Clinical Trial (n≈32) will be invited to participate in an online-facilitated in-depth interview (IDI) as part of the Screening visit (though not required to be completed on the same day as screening procedures). This interview will examine concerns, perceived barriers and challenges when invited to participate in a biomedical clinical trial to inform efforts focused on their engagement in future trials. The IDI will be conducted by a trained interviewer located at UPenn using video-conferencing.

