6.4 Visit 2 - Enrollment Visit (Day 0)

Visit 2 must take place  $\leq$ 45 days after Visit 1. If more than 45 days pass before Visit 2, participants will need to be re-screened and re-consented. If deemed eligible based on the results from the screening procedures, participants will be contacted to schedule an Enrollment visit and asked to refrain from RAI and the insertion of anything in their anorectum for 72 hours prior to the visit. YMSM will complete a baseline web-survey examining questions on participants' prior experiences and comfort using rectal products, as well as douching or other rectal hygiene practices.

Baseline samples (see Appendix 1) will be collected to establish pre-dose conditions for safety assessments as well as sample collection for TFV analyte concentration in multiple matrices for participants taking oral TDF/FTC PrEP. Prior to proceeding to Visit 3 (Dosing Visit), the participant's plasma will be analyzed for tenofovir/emtricitabine. Individuals with quantifiable tenofovir/emtricitabine concentrations will be excluded from participation in the tenofovir douche administration and pharmacokinetic sampling. These concentrations will be used to adjust post-dose PK and PD assessments. The following activities (Table 9) will take place at the Enrollment visit:

Component	Procedure/Analysis
	Confirm participant understood and signed informed consent
	Review/update locator information
	Confirm eligibility
Administrative	• Ensure participant complied with pre-visit instructions
	
 
Provide counseling and condoms:         
 
HIV/STI risk reduction counseling
 
Provide a copy of pre- and post- visit reminders
 
Participant education: flexible sigmoidoscopy procedure with biopsy & rectal fluid collections
 
 
 

	Review/update medical history
	
 
Review/update incurcat instory
 
Review/update concomitant medications
 

	
 
Complete AE assessment
 

Clinical	
 
Review any available test results
 

	
 
Perform symptom-directed physical exam, including rectal exam, as needed
 

	
 
Collect vital signs (HR, BP, temp)
 

Safety Labs: blood	• HIV-1 antigen/antibody 4 th generation testing (confirmatory tests as needed)
Cleansing Enema	• Cleansing enema will be administered, in preparation for flexible sigmoidoscopy

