# Table 9: Visit 2 – Enrollment Visit

### 6.5 Visit 3 - Dosing Visit (Day 1)

Visit 3 must take place > 7 days and  $\leq$ 21 days after Visit 2 (the Enrollment Visit) and  $\leq$ 45 days from the Screening Visit 1. Prior to using the TFV douche, baseline samples (see Appendix 1) will be collected to establish pre-dose conditions for safety assessments as well as sample collection for TFV analyte concentration in multiple matrices for participants taking oral TDF/FTC PrEP. These concentrations will be used to adjust post-dose PK and PD assessments.

YMSM will then receive a dose of the TFV douche at the research unit, and, asked to retain the douche without defecation for 5 minutes, if possible. Subsequently, participants will be instructed on how to expel the douche contents. The amount of time that the douche was retained and the volume of expelled effluent will be measured. Post-dose observations and data collection will follow at 1, 6, 24 and 72 hours, using a sparse sampling design in which paired plasma and peripheral blood mononuclear cells (PBMC) are collected at all PK sampling times.

Participants are assigned to a single time point for flexible sigmoidoscopy with rectal biopsies at either 1,6, 24, or 72 hours after dosing (thus, providing 4 subjects at each time point). Anoscopy, with rectal fluid collection will occur pre-dose and at either 1, 6, 24, or 72 hours after dosing, coinciding with each participant's flexible sigmoidoscopy. Microbiome specimens will be collected via anoscopy pre-dose and at 24 hrs post-dose.

Between sampling windows, YMSM will complete a web-survey examining their perceived reactions and comfort using the study douche, factors influencing product use in the future, and comfort with the trial procedures. The survey will be administered after dosing, but scheduled not to interfere with other study assessments. Sampling for safety, PK, PD, and acceptability assessments will be collected according to a schedule of events (see Appendix 1). A summary of the proposed activities to take place at this visit is noted below:

Component	Procedure/Analysis
	Confirm participant understood and signed informed consent
	Review/update locator information
	Confirm eligibility
Administrative	• Ensure participant complied with pre-visit instructions
Aummistrative	
 
Provide counseling and condoms:
 

	
 
HIV/STI risk reduction counseling
 

	• Provide a copy of pre- and post- visit reminders

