#### 6.12.1 Phase I Behavioral Questionnaire (Enrollment Visit)

Note: The Baseline Behavioral survey may be completed at any time from the enrollment visit (Visit 2) until just prior to TFV douche dosing on Day 1 (Visit 3).

The baseline behavioral data will be primarily descriptive of demographic variables (age, gender-identity, sexual orientation, racial background, education, and income), HIV test history and status, sexual behaviors and PrEP awareness, technology use, substance use, psychological distress and well-being, and rectal douche practices. It will assess participants' risk perception for HIV or STI transmission, and willingness to participate in biomedical trials. Baseline behavioral data will be collected via a web-based self-interview, also known as a web-based computer self-interview (WCSI), to be completed by the participant at Visit 1.

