#### Baseline evaluations/measures

- Demographic Information
- Socioeconomic
- Housing
- General Health and Well-Being
- Relationships
- HIV and STI Testing
- Sexual Behaviors & Condom Use
- PrEP Use, Awareness, and Willingness
- Technology Use and Social Media
- Substance Use
- Psychological Distress
- Willingness to participate in biomedical trials
- Rectal Douching Practices
- Motivation for Clinical Trial Participation

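### Section 9.6 plans a paired before/after test of acceptability, but no pre-dose data collection listed in the protocol includes a rating of the TFV douche

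*Combined protocol and SAP*

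**What the plan says.** **Objective.** Section 2.1 and Table 6 make it a primary objective to describe acceptability "prior to and after using a one-time dose of the Product C douche". Table 6 gives questionnaires and in-depth interviews as the endpoints.

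**Analysis.** Section 9.6 scores acceptability from 1 to 4 after administration and tests the mean against 3 with a one-sample, one-sided t-test. It adds a paired t-test of whether "acceptability of a TFV douche changed between before and after using it". Type I error is 0.10, without adjustment for multiplicity.

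**Before dosing.** The screening survey (6.3) covers sexual behaviour and "prior experiences and comfort using rectal products, and douching or other rectal hygiene practices". The enrolment survey (6.4) covers "prior experiences and comfort using rectal products, as well as douching or other rectal hygiene practices". Section 6.12.1 adds demographic, health and behavioural domains, and "risk perception for HIV or STI transmission, and willingness to participate in biomedical trials".

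**After dosing.** Of the web survey on reactions to the douche, Section 6.5 says: "The survey will be administered after dosing, but scheduled not to interfere with other study assessments". Section 6.12.2 lists product acceptability and likelihood of future use for the questionnaire given after the product has been used. Section 6.12.3 lists acceptability as a topic of the exit interview.

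**The concern.** A paired t-test works on within-person differences, so it needs the same score from the same participant on both sides of the dose. The protocol names the post-dose source and never says where the pre-dose score comes from. If the baseline survey has no such item, the gap cannot be closed later: once a participant has used the douche, any rating of what he expected is a recollection coloured by use. The planned test would then have no data, and the before-use half of a primary objective would have no quantitative score.

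**Working it through.** The main check is documentary. Each listed source was read for a rating of acceptability, or likelihood of use, of the TFV douche.

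| Source | Timing | Relevant content | Douche rating listed? |
|---|---|---|---|
| Screening survey (6.3) | before | sexual behaviour, experience with rectal products, hygiene | no |
| Screening survey (9.1) | before | similar, plus willingness to join the trial | no |
| Enrolment survey (6.4) | before | experience with rectal products, hygiene | no |
| Baseline survey text (6.12.1) | before | demographics, behaviour, risk perception, trial willingness | no |
| Baseline domain list (6.12.1) | before | 14 domains | no |
| Dose Acceptability Questionnaire (6.12.2, Appendix I) | after, Visit 3 only | 6 domains, including acceptability and likelihood of use | yes |
| Exit interview (6.12.3, Appendix I) | after, Visit 6 | acceptability as a topic | qualitative only |

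The closest pre-dose domain is "PrEP Use, Awareness, and Willingness". It does not name the douche. Willingness to join trials and douching practices are different constructs. Nothing in the documents maps any of these domains to the 4-point score in 9.6.

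**Number of pairs.** Pairs = participants with both scores. The planned enrolment is 16 and the number of before scores listed is 0, so pairs as listed = 0. The imputation methods in 9.7 do not help, because they all draw on observed values and an item nobody was asked has none.

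**What the paired test could show if the item exists.** The plan gives no power for acceptability, so there is no figure to reproduce. Assume a two-sided test (the sidedness is not stated) and use the noncentral t with noncentrality d√n, where d is the mean change in SDs of the change. With 16 pairs at 0.10, 80% power needs d = 0.65. With 14 pairs it needs d = 0.70. At d = 0.5 with 16 pairs, power is 0.60. This is a modest test, and lost pairs reduce it further.

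**Related wording in 9.7.** Section 9.7 ends by saying that familywise corrections will be used, and names no tests or method. Applying this to acceptability would change little. As an illustration, assume Bonferroni over the two acceptability tests (0.10/2 = 0.05 each) and SD 0.8. The one-sample cut-off is 3 + t × SD/√16, with 15 degrees of freedom:

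- at 0.10: 3 − 1.341 × 0.8/4 = 2.73
- at 0.05: 3 − 1.753 × 0.8/4 = 2.65

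Across SDs of 0.6 to 1.0, the two rules give different one-sample conclusions in 3.7–15.5% of trials when the true mean is 2.5 to 3.0, and in 0.1–0.7% when it is 3.25. Without adjustment, the chance of at least one false rejection over the two tests is 1 − 0.9² = 0.19 if they are independent, and at most 0.20.

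**The case against.** The strongest reply is that the protocol lists domain headings, not items. Section 1.6 reports that DREAM-01 recorded anticipated likelihood of use at baseline (15 of 17 likely or very likely), and 9.6 says that major parts of the survey come from earlier trials. A matching item may well sit under one of the baseline headings. This stands. A reader might infer that pre-dose acceptability will not be collected, and the documents do not show that. They show that the before score is not named. The lists in 6.12 are nevertheless detailed enough to name acceptability after dosing, and the baseline list omits it.

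The second reply is that the paired test is an additional analysis in an exploratory study of 16. This also stands. A reader might infer that the main acceptability conclusion is at risk, but the one-sample test uses only the post-dose score. The exit interview may also give a retrospective, qualitative account of expectations. It cannot supply the before score for a t-test.

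Two further readings go too far. Sections 9.6 and 9.7 might be taken as a contradiction on multiplicity. However, 9.6 states a specific rule for acceptability, while the general sentence in 9.7 can apply elsewhere, for instance to the PK comparisons by age group and with DREAM-01. Section 6.12.1 also gives two times for the baseline survey: from Visit 2 until just before dosing, and "to be completed by the participant at Visit 1". Both times are before dosing, so pairing does not depend on which is meant.

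**Conclusion.** The point holds as a gap between a planned analysis and the data collection listed for it. The primary objective and the paired t-test need a before-use acceptability score, and no pre-dose survey content or schedule row names one. As listed, the test has 0 of 16 possible pairs. The actual number depends on questionnaires that are not in the documents. If the item is missing, the loss is permanent for each participant dosed. It is confined to the paired test and the before-use half of the quantitative objective. The 9.7 wording and the survey timing are minor clean-ups. The figures given for 9.7 rest on an assumed SD, family and correction method, and carry no weight in this conclusion.

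**What to change.** 1. Check the Baseline Behavioral Survey before enrolment.
   - If a matching item is there, name it in 6.12.1 and Appendix I.
   - If it is not, add an anticipated version of the post-dose item that supplies the 9.6 score. Use the same 4-point response anchors and one fixed wording, have it completed before dosing, and list it in both places.
   - If no matching item can be collected, drop the paired test and the before-use part of the quantitative objective.
2. Limit the paired test to participants with both scores, report how many there are, and state whether the test is one- or two-sided.
3. In 9.7, say that the familywise sentence does not apply to the acceptability tests governed by 9.6, and name the comparisons and method it does cover. Do not simply delete it, since it may be the only multiplicity rule for the PK comparisons.
4. Give one completion time for the baseline survey in 6.12.1.

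The cost is a slightly longer baseline survey and short edits to 6.12.1, 9.6, 9.7 and Appendix I. Keeping the acceptability tests unadjusted leaves their joint error rate above 0.10, which 9.6 already accepts.
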